3.2 Study Population

Definition of non-sustained response to previous therapy

Subjects will be considered as having non-sustained response to previous therapy if they received any interferon based therapy with or without ribavirin for any duration. Subjects whose HCV RNA remained detectable throughout therapy (non-responders) and those whose HCV RNA dropped below detectability during treatment but became detectable while still on therapy (break-through) or once therapy was discontinued (relapsers) will be eligible for participation. All genotypes will be eligible provided they meet the above virological definitions.

3.3 Entry Criteria

Inclusion Criteria

To be eligible for this trial, patients must meet the following inclusion criteria:

- Age at least 18 years at screening
- Serum HCV RNA above quantifiable level of detection by any assay after the end of previous therapy
- ALT > 65 IU/L (i.e., approximately 1.5 X upper limit of normal) obtained during the screening period
- Previous treatment with any interferon-based therapy without sustained virological response
- Negative urine pregnancy test (for women of childbearing potential) documented within the 24-hour period prior to the first dose of silymarin. Females of childbearing potential must be using two reliable forms of effective contraception during the study (while on drug and during follow-up)

Exclusion Criteria

Patients with any of the following will not be eligible for participation:

- Use of silymarin or other milk thistle preparations within 30 days prior to screening
- Use of other antioxidants such as vitamin E, vitamin C, glutathione, alpha-tocopherol, or non-prescribed complementary alternative medications (including dietary supplements, megadose vitamins, herbal preparations, and special teas) within 30 days prior to screening. A multivitamin at standard doses will be allowed.
- Use of silymarin or other antioxidants or non-prescribed complementary alternative medications (as above) during the screening period or patient unwilling to refrain from taking these medications through completion of the study.
- Any antiviral therapy within 6 months prior to screening visit
- Known allergy/sensitivity to milk thistle or its preparations
- Evidence of poorly-controlled diabetes (defined as HbA1c > 8% in patients with diabetes)
- Use of warfarin, metronidazole or acetaminophen (greater than two grams per day) within 30 days of screening
- Lactose intolerance defined as patient reported inability to tolerate milk products
- Previous liver biopsy that demonstrated presence of moderate to severe steatosis or evidence of steatohepatitis
- Positive test for anti-HIV or HBsAg within 5 years of screening
- Average alcohol consumption of more than one drink or equivalent (>12 grams) per day or more than two (2) drinks on any one day over the 30 days prior to screening. Patients who met either criterion more than 30 days ago must have consumed a monthly average of 12 grams or less per day of alcohol for at least six months prior to screening.

- History of other chronic liver disease, including metabolic diseases, documented by appropriate test(s)
- Women with ongoing pregnancy or breast-feeding, or contemplating pregnancy
- Serum creatinine level 2.0 mg/dL or greater at screening or CrCl ≤ 60cc/min, or currently on dialysis. The creatinine clearance (CrCl) will be calculated according to Cockcroft-Gault.
- Evidence of drug abuse within 6 months prior to screening or during the screening period.
- Evidence of decompensated liver disease defined as any of the following: serum albumin <3.2 g/dl, total bilirubin > 1.5 mg/dl, or PT/INR > 1.3 times normal at screening, or history or presence of ascites or encephalopathy, or bleeding from esophageal varices
- History or other evidence of severe illness or any other conditions that would make the patient, in the opinion of the investigator, unsuitable for the study (such as poorly controlled psychiatric disease, coronary artery disease, or active gastrointestinal conditions that might interfere with drug absorption)
- History of immunologically mediated disease (e.g., inflammatory bowel disease, idiopathic thrombocytopenic purpura, lupus erythematosus, autoimmune hemolytic anemia, severe psoriasis, rheumatoid arthritis) that could affect inflammatory biomarkers
- History of solid organ or bone marrow transplantation
- History of thyroid disease poorly controlled on prescribed medications
- Use of oral steroids for more than 14 days within 30 days prior to screening
- Participation in a research drug trial, exclusive of the SyNCH Phase I trial, within 6 months of enrollment
- Inability or unwillingness to provide informed consent or abide by the study protocol

3.4 Study Treatment

All eligible participants will be randomized to treatment with either Legalon[®] 420 mg, or 700 mg or placebo administered thrice daily. The treatment period will be for 24 weeks and subjects will be followed off treatment for an additional 12 weeks. An IND (#74887) has been filed for the use of Legalon[®] in this study and a dossier reflecting additional preclinical and clinical information about this agent accompanies this protocol (Appendix 3).

Each patient will receive a total of 5 capsules as outlined in Table 2 for each orally administered dose that will consist of Legalon[®] and/or placebo in the appropriate capsule quantities in order to standardize pill burden, allow for an estimate of compliance, and to minimize the potential for variable absorption due to differential solubility in the gastrointestinal tract.

Legalon[®] (Rottapharm/Madaus) is a milk thistle fruit extract standardized to 140 mg silymarin per capsule (53% as total silybins). A Legalon[®] 140 capsule contains 180 mg dried extract of milk thistle fruits, or 140 mg silymarin which is the presumed active ingredients, or 108 mg silymarin quantitated as silybin by HPLC. The total weight of the capsule is 429 mg and includes: other milk thistle components that are not chemically well defined; components of the extraction process; excipients; and the capsule shell. The 108 mg of silymarin in Legalon[®] 140 capsules consists of the following potentially active ingredients: silybins A + B (~50 mg), silychristin (~20 mg), silydianin (~15mg), and isosilybins A + B (~15 mg).

	Dosing offategy for off	andaraizing r in Durden	
Legalon [®] Dose	# Legalon [®] Caps	# Placebo Caps	Total # of Capsules
Placebo	0	5	5
420 mg	3	2	5
700 mg	5	0	5

Table 2 Dosing Strategy for Standardizing Pill Burden

3.4.1 Dose Adjustment Guidelines

Specific dose adjustment guidelines are provided to investigators for adverse effects considered to be possibly related to silymarin, including laboratory abnormalities, adverse events, and vital signs changes. Investigators should utilize the "General Dose Reduction Guidelines" (Section 3.4.2) below. When practical, abnormal laboratory results should be confirmed as soon as possible following notification of the investigator. If appropriate, downward adjustments in one level increment (see below) should be considered.

3.4.2 General Dose Reduction Guidelines

Dose reduction will be based upon severity ratings in accordance with the Common Toxicity Criteria for Adverse Events (CTCAE) (Appendix 4). Reporting of an abnormal ALT/AST results remains at the discretion of the clinical center Principal Investigator.

For grade 1, no dose reduction is needed. For grade 2 that persists over two consecutive safety visits and is not responsive to adjunctive symptomatic management, a level 1 dose decrease of study medication may occur at the discretion of the investigator. For grade 3 not responsive to adjunctive measures, a level 1 dose decrease of study medication is required. Subjects with grade 3 should be followed closely, possibly at more frequent intervals or via telephone contact to monitor in between regularly scheduled safety visits. If symptoms improve, return to previous dosing is allowed at the discretion of the investigator. For grade 4, treatment will be discontinued. It should be noted that certain toxicities carry different levels of significance for each patient and therefore, the investigator should use these as guidelines only, within the context of clinical judgment.

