2.3 Endpoints

Efficacy: The primary outcome variable (endpoint) for efficacy is whether or not serum ALT (mg/dl) is \leq 45 IU/L (approximate normal range) or achieves at least 50% decline to less than 65 IU/L (approximately 1.5 times the upper limit of normal) at the end of the 24-week treatment period. The relationship between dose and change in log₁₀(ALT) will also be investigated as a part of secondary analysis plans.

Safety: The primary outcome variable for safety is the occurrence of a dose-limiting toxicity during the 24-week treatment period. All adverse events (AE) will be categorized by severity.

Adherence: Will be measured using a summary of missed dose information obtained from patient diaries and dose counts and will be analyzed as both an outcome and as an explanatory variable in exploratory analyses of pharmacokinetic exposure and response.

Biomarkers: The following relationships will be explored: dose and change in biomarkers, changes in biomarkers and rate of treatment success, changes in biomarkers and rate of toxicity.

Rationale for using serum ALT and not liver biopsy as an endpoint:

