3.4.3 Dose-Specific Reduction Guidelines

AE Grade	Reduction?	Discontinue?	Silymarin	Placebo	Pill Burden
Mild	No	No	5	0	5
Moderate*	Yes	No	4	1	5
Severe**	Yes	Temp	3	2	5
Life Threatening	No	Yes	0	0	0

Dose Reduction Guideline – Silymarin 700 mg dose level

Dose Reduction Guideline – Silymarin 420 mg dose level

AE Grade	Reduction?	Discontinue?	Silymarin	Placebo	Pill Burden
Mild	No	No	3	2	5
Moderate*	Yes	No	2	3	5
Severe**	Yes	Temp	1	4	5

Life Inreatening No Yes 0 0 0

*Moderate AE: Patient can resume original dose level if AE improves or resolves. NOTE: If the subject experiences a drug related AE and two dose reductions are not tolerated, the subject will stop the drug

**Severe AE: Discontinuation for 1 week. If SAE improves or resolves, restart at indicated dose level at the investigator's discretion. The dose level may be increased to original dose level at the discretion of the investigator with continued close monitoring.

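### Sections 3.4.2 and 3.4.3 give different dose-reduction instructions for the same grade 3 event, and different triggers for grade 2, with 'level' left undefined

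*Protocol*

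**What the plan says.** Section 3.4.1 sends investigators to section 3.4.2 and speaks of downward adjustment by one level, without saying what a level is.

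Section 3.4.2 works by CTCAE grade:

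- **Grade 2.** The trigger is "For grade 2 that persists over two consecutive safety visits and is not responsive to adjunctive symptomatic management". Once it is met, "a level 1 dose decrease of study medication may occur at the discretion of the investigator".
- **Grade 3.** "For grade 3 not responsive to adjunctive measures, a level 1 dose decrease of study medication is required". No interruption is mentioned.
- The section closes by telling investigators to treat these rules as guidance, subject to clinical judgment.

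Section 3.4.3 gives one table per active dose, with rows by severity and columns for reduction, discontinuation and capsule counts:

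- **Moderate, 700 mg table.** "Moderate* Yes No 4 1 5": a reduction, no discontinuation, four silymarin capsules and one placebo.
- **Severe, 700 mg table.** "Severe Yes Temp 3 2 5": a reduction, a temporary discontinuation, three silymarin capsules.
- **Severe, 420 mg table.** "Severe Yes Temp 1 4 5": the same actions, one silymarin capsule.
- **Severe footnote.** "Severe AE: Discontinuation for 1 week", then a restart at the tabulated count at the investigator's discretion. The condition for restarting is written in terms of an SAE improving or resolving.
- **Moderate footnote.** It allows a return to the original dose. It also stops the drug when a drug-related event occurs and two dose reductions are not tolerated.

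**The concern.** Dose-modification rules belong in the protocol, and sites need one default from which to exercise judgment. Here an investigator facing a grade 3 event finds two defaults that differ in trigger, size of reduction and whether treatment is paused. For grade 2 the two defaults differ in trigger.

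Three things are at stake:

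- the consistent handling of patients with severe events;
- the silymarin dose actually received, which feeds the exposure-response analyses in sections 6.2 and 6.4;
- the decision to stop treatment. The footnote in 3.4.3 counts dose reductions, and section 3.5 allows discontinuation for intolerance despite predetermined reductions. Neither can be applied uniformly while it is unclear what counts as a reduction.

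The severe-event footnote adds a smaller difficulty. Section 7.5 defines seriousness separately from severity, and a grade 3 event need not be serious. Read literally, the restart condition does not cover a severe but non-serious event.

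**Working it through.** No sample size, power or alpha figure in the protocol rests on these rules, so there is no stated figure to reproduce. The check is a side-by-side reading followed by capsule arithmetic.

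**Step 1: matching the rows.** The tables use mild, moderate, severe and life-threatening under a column headed as the AE grade; the text uses CTCAE grades 1 to 4. That moderate means grade 2 and severe means grade 3 is not written out. The column header and the CTCAE basis imply it, and the two ends of the scale agree: no change for mild/grade 1, discontinuation for life-threatening/grade 4.

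**Step 2: side by side.**

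| | Section 3.4.2 | Section 3.4.3 |
|---|---|---|
| Grade 2 trigger | persistence over two visits and non-response | none stated |
| Grade 2 action | level 1 decrease, discretionary | reduction marked Yes |
| Grade 2 size | level 1 | one capsule (5 to 4; 3 to 2) |
| Grade 3 trigger | non-response to adjunctive measures | none stated |
| Grade 3 action | level 1 decrease, mandatory | reduction plus one-week stop |
| Grade 3 size | level 1 | two capsules (5 to 3; 3 to 1) |

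**Step 3: can a definition of 'level' reconcile them?** The text gives grades 2 and 3 the same level 1 step. The tables give them different steps.

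- If level 1 is one capsule, grade 2 agrees in size and grade 3 does not.
- If level 1 is two capsules, grade 3 agrees in size and grade 2 does not.
- Under either meaning, the differences in trigger and the one-week stop remain.

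**Step 4: size, assuming one level is one capsule.** Section 3.4 gives 140 mg silymarin per capsule. Dose per administration = capsules × 140 mg.

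| Arm | Assigned | Grade 3 by 3.4.2 | Grade 3 by 3.4.3, after a one-week stop |
|---|---|---|---|
| 700 mg | 5 × 140 = 700 | 4 × 140 = 560 (1/5 = 20% lower) | 3 × 140 = 420 (2/5 = 40% lower) |
| 420 mg | 3 × 140 = 420 | 2 × 140 = 280 (1/3 = 33% lower) | 1 × 140 = 140 (2/3 = 67% lower) |

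In the 420 mg arm the two readings differ by a factor of 280/140 = 2. In the 700 mg arm the tabulated restart dose equals the assigned dose of the low-dose arm. The stop itself is 1/24 = 4.2% of the treatment period.

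**Step 5: the stopping rule.** By the table, one severe event in the 420 mg arm takes a patient from 3 capsules to 1, the lowest non-zero count listed. The protocol does not say whether that is one reduction or two, so the rule in the moderate footnote can be counted either way.

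**The case against.** The strongest reply is that section 3.4.2 calls its rules guidance, the tables are themselves titled as guidelines, restart is discretionary, and both sections allow a return to the earlier dose. This softens the conflict but does not remove it. The same paragraph makes the grade 3 decrease mandatory, and judgment still needs a single default to depart from.

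A second reply concerns grade 2. Since 3.4.1 points to 3.4.2 for the decision, the tables can be read as giving only the capsule counts once a reduction has been decided. On that reading a site can follow both sections, and with one level as one capsule the size agrees. This largely stands: the grade 2 limb is a milder conflict, about the trigger. The reading does not rescue grade 3, where size and interruption both differ.

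A reader might go further and infer that the primary safety outcome inherits the conflict, because section 2.3 says "The primary outcome variable for safety is the occurrence of a dose-limiting toxicity during the 24-week treatment period". The documents do not support that. The protocol text does not define dose-limiting toxicity, and section 6.1 compares toxicity rates without reference to dose reductions. A definition by grade and relatedness would be untouched; only one based on the dose action taken would be affected.

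Nor can the effect be sized by multiplying 51 patients by 0.05. Section 6.1 offers 0.05 as an upper figure for the background rate without silymarin, not as the expected rate in every arm; its power scenario puts both silymarin arms at 0.10. Managing an event differently does not change whether it occurred.

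It would also be too strong to say that results would vary by site rather than by drug. Allocation is stratified by site, treatment is masked and the main efficacy analysis is ITT, so site habits should be roughly balanced across arms.

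**Conclusion.** The point holds as an internal inconsistency. For grade 3 the two sections conflict in trigger, size of reduction and interruption, and no definition of 'level' reconciles them. For grade 2 they differ in trigger and in whether the reduction is discretionary.

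The size is 560 mg against 420 mg per dose in the 700 mg arm and 280 mg against 140 mg in the 420 mg arm, with a one-week stop under one reading only. These figures assume that one level is one capsule, the natural inference from the tables but not stated. The comparison also rests on the implied match of moderate to grade 2 and severe to grade 3.

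The consequences that can be shown are for handling of severe events, dose received and the stopping rule. An effect on the primary safety outcome is conditional on a definition that the protocol does not give, and is not claimed here.

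**What to change.** Reconcile sections 3.4.1, 3.4.2 and 3.4.3 so that each grade has one trigger, one number of levels and one interruption rule, stated identically in text, tables and footnotes. Define 'level' in capsules, and state how a two-capsule step counts towards the rule that stops treatment after failed reductions. Write out how the severity labels map to CTCAE grades. Replace SAE in the severe-event footnote with the intended term. Which of the conflicting rules is to apply is for the clinical team.

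This does not require defining dose-limiting toxicity by the dose action. Doing so would make a primary outcome depend on a partly discretionary decision.

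The cost is a protocol clarification or amendment and a memo to the sites. No additional data are needed, and the sample size and planned tests are unaffected.

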3.4.3 Dose-Specific Reduction Guidelines

AE Grade	Reduction?	Discontinue?	Silymarin	Placebo	Pill Burden
Mild	No	No	5	0	5
Moderate*	Yes	No	4	1	5
Severe**	Yes	Temp	3	2	5
Life Threatening	No	Yes	0	0	0

Dose Reduction Guideline – Silymarin 700 mg dose level

Dose Reduction Guideline – Silymarin 420 mg dose level

AE Grade	Reduction?	Discontinue?	Silymarin	Placebo	Pill Burden
Mild	No	No	3	2	5
Moderate*	Yes	No	2	3	5
Severe**	Yes	Temp	1	4	5

Life Inreatening No Yes 0 0 0

*Moderate AE: Patient can resume original dose level if AE improves or resolves. NOTE: If the subject experiences a drug related AE and two dose reductions are not tolerated, the subject will stop the drug

**Severe AE: Discontinuation for 1 week. If SAE improves or resolves, restart at indicated dose level at the investigator's discretion. The dose level may be increased to original dose level at the discretion of the investigator with continued close monitoring.

3.4.4 Safety measurements

Laboratory evaluations: Participants will undergo laboratory tests according to the time and event schedule to monitor for medication toxicities.

Adverse event monitoring: Participants will be queried by study personnel at each study visit about the incidence of adverse events. These will be documented in the study record and classified according to duration, severity, relationship to study medication, and action with study medication. Serious adverse events will be reported to appropriate regulatory authorities, in addition to the DSMB as below, in a timely fashion.

In the event that an investigator considers an adverse event to be related to study medication, the investigator may submit an unmask request to the clinical center investigational pharmacist to unmask the study drug dose, per the study specific unmasking procedure.

Pregnancy: Women of child-bearing potential will have a urine pregnancy test performed within 24 hours of the first administration of study drugs, monthly for the duration of therapy, and at 1 month following completion of therapy.

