This proposal is a phase II study that will evaluate the safety and efficacy of silymarin for the treatment of subjects with chronic hepatitis C who did not respond to conventional antiviral therapy. The primary objectives of this study are to assess the safety and adverse event profile of silymarin over a range of doses compared to placebo and to assess efficacy of silymarin in normalizing serum aminotransferase activity in patients with chronic hepatitis C. Secondary objectives are to characterize the effect of silymarin on serum levels of HCV RNA and to explore relationships between silymarin therapy and serum biomarkers of HCV hepatic disease activity (oxidative stress, apoptosis, and fibrogenesis).

Eligible subjects will be randomized to treatment with placebo or one of two dosages selected from the phase I study: Legalon[®] 420 mg or 700 mg administered orally thrice daily.

Investigators and subjects will be masked to treatment assignment. The study design includes a screening period during which patients will undergo full medical evaluation to verify protocol eligibility and a treatment period of 24 weeks during which time clinic visits and laboratory studies will be performed every 2-4 weeks to monitor for safety and efficacy of therapy. Subjects will continue to be followed for an additional 12 weeks after the completion of study medication to monitor for adverse events and investigate post-treatment outcomes. Blood will be collected for pharmacokinetic analysis for confirming estimates of PK parameters obtained during phase I, for measuring biomarkers, and for storage for future studies.

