- 3) Unexpected

All deaths will be subject to expedited reporting, regardless of whether they are considered unexpected or related to medicinal product.

Related to Medicinal Product

The phrase "**related to the medicinal product**" implies causality or attributability to Legalon[®]. An adverse event should be considered to be related to Legalon[®] in situations in which a causal relationship cannot be ruled out. As noted above, the clinical center PIs will assess the degree of relatedness of the study medications and adverse events (i.e., unrelated, possibly related, probably related, definitely related).

Unexpected

The term **unexpected** refers to an adverse event that has not been previously observed or documented. A guideline is needed to define an adverse event as either expected or unexpected based on previous observation. The following documents or circumstances will be used to determine the expectedness of an adverse event:

- The Drug Label which contains the clinical and non-clinical data on therapy with Legalon[®].
- The natural history of chronic hepatitis C.
- Reports, which add significant information on specificity or severity of an otherwise known and documented adverse event, associated with the use of Legalon[®]. Thus more severe or more specific adverse events than had previously been observed are considered unexpected.

Expedited reporting is also required when there is an increased rate of occurrence of expected, serious adverse events related to the medicinal product. Hence, the DCC will prepare reports of rates of serious adverse events for review at DSMB calls and meetings.

Sufficient data on adverse events requiring expedited reporting must be obtained by clinical center personnel to enable clinical center personnel to complete the MedWatch form (FDA Form 3500A).

The DCC will send copies of the initial notification and written reports on adverse events to the NCCAM and NIDDK project scientists, the Chairperson of the DSMB, the other clinical centers,

and Rottapharm/Madaus. The Data Coordinating Center Principal Investigator, project coordinator, and data managers will be notified of serious adverse events.

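### An investigator's opinion that an adverse event is drug-related is the only stated ground for an unmask request, with no severity or need-for-care condition

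*Protocol*

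**What the plan says.** The opening summary states: "Investigators and subjects will be masked to treatment assignment". Section 3.1 calls the study double-masked.

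Section 3.4.4 (adverse event monitoring) sets out the route to unmasking. The condition is "In the event that an investigator considers an adverse event to be related to study medication". The permission is that "the investigator may submit an unmask request to the clinical center investigational pharmacist to unmask the study drug dose". The sentence ends with the qualifier "per the study specific unmasking procedure". That procedure is not reproduced in the protocol.

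Section 7.5 defines relatedness: "An adverse event should be considered to be related to" Legalon "in situations in which a causal relationship cannot be ruled out". The same section says that "the clinical center PIs will assess the degree of relatedness of the study medications and adverse events", on a four-step scale that runs from unrelated to definitely related.

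Safety is primary objective 1 (section 2.1). Section 2.3 defines its outcome: "The primary outcome variable for safety is the occurrence of a dose-limiting toxicity during the 24-week treatment period".

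Section 3.4.2 ties dose changes to CTCAE severity and asks for none at grade 1. In the section 3.4.3 tables, every reduced level still totals five capsules.

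**The concern.** A double-masked trial needs a way to break the mask for an individual patient. The ground normally expected is that knowing the assignment matters for that patient's care. Section 3.4.4 names a different ground: the investigator's opinion that the event is related. On its wording, a mild, short-lived event is enough for a request if causality cannot be excluded.

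The person who then learns the arm may go on to judge that patient's events. Three things are at stake:

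- revision of the triggering event's severity, attribution, action or outcome;
- grading and attribution of the same patient's later events;
- later dose and discontinuation decisions, which sections 3.4.2 and 3.5 leave partly to the investigator's judgement.

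These judgements can feed the safety results. Because suspected drug effects trigger the requests, unmasking may also be more frequent in some arms than in others.

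**Working it through.** **1. Is the breadth needed by the protocol's own dose rules?** Set side by side:

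- Section 3.4.4: the trigger is relatedness, at any severity.
- Section 3.4.2: dose action depends on severity, and grade 1 calls for none.
- Section 3.4.3: reduced levels are 4 + 1 and 3 + 2 capsules (silymarin + placebo) from the 700 mg dose, and 2 + 3 and 1 + 4 from the 420 mg dose. Each totals 5.

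A reduction therefore does not show in the capsule count. The text does not say who changes the capsule mix, so it is an inference that this can be done without telling the investigator the arm. Nothing in these sections requires the investigator to know the arm for every related event.

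**2. The protocol's own safety figure.** Section 6.1 gives 12% power for a three-arm chi-square test with toxicity rates 0.05, 0.10 and 0.10 at α = 0.05. Section 6.3 gives 51 patients per arm.

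- Mean rate: (0.05 + 0.10 + 0.10)/3 = 0.0833.
- Noncentrality: n × Σ(pᵢ − p̄)² / [p̄(1 − p̄)] = 51 × 0.001667 / 0.07639 = 1.11, on 2 degrees of freedom.
- Power: 14.3% by the noncentral chi-square approximation, and 13.0% by simulation of the Pearson test (400,000 trials).

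The simulated value is within about one point of the stated 12%. This point disputes no stated figure.

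**3. What one judgement is worth.** In the section 6.1 scenario, the expected toxicities are:

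- placebo: 51 × 0.05 = 2.55;
- each silymarin arm: 51 × 0.10 = 5.1;
- total: 2.55 + 2 × 5.1 = 12.75.

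One event reclassified in one arm moves that arm's rate by 1/51 = 1.96 percentage points. The scenario's contrast is 0.10 − 0.05 = 5 points, so one event is 1.96/5 = 39% of it.

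**4. How many requests?** The protocol gives no number. Two assumed scenarios show the scale; neither is a bound.

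- *Phase I rate.* Section 1.0 (dose selection) reports 5 adverse events in 4 of 30 Legalon patients. Four were thought unrelated and one possibly related. That gives 1/30 × 102 = 3.4, or about 3 of the 102 silymarin patients.
- *One request per toxicity in the section 6.1 scenario.* 12.75, or about 13 of 153.

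Related events that are not dose-limiting would raise the second count. Events for which nobody submits a request would lower it.

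**5. Which judgements are exposed?** Relatedness must be judged before a request can be made, so that first call is masked. Exposure begins on release of the assignment and covers revisions and later events in that patient.

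**The case against.** The strongest reply is that section 3.4.4 provides for a request, not a release, and refers to a study-specific procedure. That procedure may already require clinical need, approval and a log. This stands: a reader might infer that relatedness alone opens the mask, or that no safeguard exists, and the protocol shows neither. What remains is that the protocol itself states the ground for asking, and states it broadly. If the procedure is narrower, the two texts should agree.

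Other replies also stand in part:

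- A reader might infer that most adverse events would qualify. The only data in the protocol point the other way, with four of five phase I events judged unrelated. Thirty patients are a weak guide, but there is no support for a higher figure.
- A reader might see a contradiction with the promise of masking. Provision for unmasking an individual is compatible with a masked trial. The issue is the breadth of the ground.
- CTCAE grading limits subjectivity. It does not remove it, because section 3.4.2 tells investigators to treat the toxicity rules as guidelines within clinical judgement.
- The rates 0.05 and 0.10 are power-scenario inputs (a possible upper background rate and the maximum tolerated rate), not predictions. Section 6.1 anticipates low toxicity.
- Section 6.1 says that the test of equal toxicity rates is not a primary hypothesis. No confirmatory error rate is at risk.

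**Conclusion.** The point holds as a cheap improvement to a stated rule. The ground for an unmask request is broader than the protocol's dose rules need, and it exposes later investigator judgements in a trial whose first primary objective is safety. The harm is possible bias in descriptive safety estimates and attribution. Its direction cannot be derived from the protocol.

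The likely number of unmaskings is unknown. The scenarios of about 3 of 102 and about 13 of 153 rest on the phase I rate carrying over and on one request per toxicity at the section 6.1 rates. With so few expected events, one changed classification moves an arm's rate by about 2 points.

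A reader might also infer that the ALT endpoint is compromised. The protocol does not support that. ALT is a laboratory value, and section 3.5 calls for the week 24 data and samples from patients who stop early. The remaining route is indirect: knowledge of the arm could influence discontinuation, and section 6.3 carries the last ALT forward for dropouts.

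**What to change.** In section 3.4.4, and consistently in the study-specific unmasking procedure:

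1. Replace relatedness as the trigger. The assignment is released only when knowing it is needed for the patient's care.
2. Record severity and relatedness of the event before release.
3. Log the date, reason and recipient of each release.
4. Report unmaskings by arm. Keep all events in the main safety analysis and flag those graded after unmasking.

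Events graded after unmasking should not be excluded, even in a repeat analysis offered as the cleaner one. They are selected by a post-randomisation trigger tied to the outcome. Dropping them while keeping the patients in the denominator would lower the rates, most in the arm with more unmasking.

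The cost is one paragraph in the protocol, a matching check of the procedure and a small logging burden. Investigators lose discretionary unmasking where the assignment does not affect care. Urgent unmasking remains available, and no dose rule changes.
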